C. Secondary Objective:

i. To investigate the impact of SVG harvesting techniques – OVH vs. EVH on MACE, a composite endpoint of all-cause mortality, nonfatal myocardial infarction and repeat revascularization, at one and three-year postoperatively .

ii. To investigate the impact of SVG harvesting techniques – OVH vs. EVH on MACE, a composite endpoint of all-cause mortality, nonfatal myocardial infarction and repeat revascularization, over the entire follow-up period (active and passive) of the study postoperatively.

D. Secondary Hypothesis:

i. One-year composite MACE rate will be 6 percentage points lower in the open harvesting group and three-year composite MACE rates will be at least 8-10 percentage points lower in the open vein harvesting group compared to the endoscopic vein harvesting group.

ii. A significant smaller proportion of CABG subjects with SVGs harvested by open technique will experience MACE post-surgery compared to CABG subjects with SVGs harvested by endoscopic technique during the entire follow-up period

Other objectives are:

1. Investigate the impact of the two harvesting techniques - open vs. endoscopic - on clinical indicators of leg wound complications and subject satisfaction at six-weeks post-surgery; The hypothesis is the leg wound complications will be lower and satisfaction will be higher in the EVH group compared to OVH group.
2. Compare subject quality of life scores according to the SVG harvest technique at six-week post-surgery; the hypothesis is the subjects' quality of life scores will be higher in the EVH group compared to the OVH group.
3. Determine the role of vein harvester experience on clinical outcomes

IV. Importance of the Study Topic to the VA and Its Patients

CABG is the most common major surgical procedure in the U.S. and the VAMC Health System, and EVH is now the preferred modality of SVG harvesting in both the private sector and the VAMC (72%

EVH adoption rate in the VHA based on a 2009 survey commissioned by [name] at VACO). Decisions regarding the choice of coronary revascularization (CABG vs. percutaneous coronary intervention [PCI]) rest primarily on the anticipated failure rate of CABG versus PCI. The recent ARTS II trial (Serruys 2010) showed comparable freedom from MACE in selected patients undergoing multi-vessel PCI versus CABG.

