In the ROOBY study (CSP # 517) (Shroyer 2009), one year MACE rates were 9.9% in the OVH group and 15.3% in the EVH group ($p=0.0025$). The executive committee for the REGROUP study assumes that during the REGROUP study, 15.5% of the subjects in the EVH group will experience MACE in the first year post surgery. The committee also expects a 6 percentage point improvement in the one-year MACE rate in the OVH group.

B. Sample size calculation for the REGROUP study

To detect the expected 6 percentage point difference in one-year MACE rates between EVH (15.5%) and OVH (9.5%), a sample size of **545 in each group** will be required at 85% power, 5% type-I error rate and with a two-sided test. A sensitivity analysis was also done with various scenarios which are shown in the Table 3. Since, it would be possible to capture the majority of the MACE from the VA databases even if the subjects drop out before the one-year clinic visit, a relatively small inflation factor of 5% is used to inflate the sample size to account for the drop-outs. Approximately, 1150 subjects need to be randomized in the study to achieve the said power.

	Case 1	Case 2	Case 3	Case 4	Case 5	Case 6	Case 7	Case 8	Case 9
Tails	2	2	2	2	2	2	2	2	2
Proportion 1 (%)	9.9	9.9	9.9	9.5	9.5	9.5	10	10	10
Proportion 2 (%)	15.3	15.3	15.3	15.5	15.5	15.5	16	16	16
Alpha	0.05	0.05	0.05	0.05	0.05	0.05	0.05	0.05	0.05
Power (%)	90	85	80	90	85	80	90	85	80
Allocation ratio	1:1	1:1	1:1	1:1	1:1	1:1	1:1	1:1	1:1
Sample Size	792	677	592	637	545	476	659	563	492
Total Sample Size	1584	1354	1184	1274	1090	952	1318	1126	984
Attrition = 5%	1667	1425	1246	1341	1147	1002	1387	1185	1036
Attrition = 10%	1760	1504	1316	1416	1211	1058	1464	1251	1093
Attrition = 15%	1864	1593	1393	1499	1282	1120	1551	1325	1158

Table 3: Various sample size scenarios for the REGROUP study

Based on the one-year MACE rate difference between EVH and OVH groups as obtained from CSP 517, if we assume at the end of the active follow-up period (approximately 4.5 years from the beginning of the recruitment process) difference in survival rates (i.e., the proportion of subjects who will not experience

MACE) between the two harvesting groups will be approximately 8 percentage point (i.e., 83.5% in the EVH and 91.5% in OVH), a sample size of 532 per group will be required to achieve a power of 97.5%. So, the sample size of 1150 (with approximately 7% attrition rate accounted for) will provide adequate power to the time-to-MACE event primary outcome.

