C. Duration of Study/Number of Participating Sites

Based on the experience of previous CSP studies on CABG performed in the last decade (2000-2010) (e.g. CSP #517 ROOBY and CSP #474 RADIAL), a two subject/month/site enrollment rate was assumed to be a reasonable enrollment rate for this study. With this assumption, various scenarios were created to find an optimum balance between the number of sites, the study duration (which includes enrollment period and follow-up period) and the estimated budget. The chosen scenario was with 16 sites around the country where both EVH and OVH are currently practiced. With 16 sites and two subjects/month/site rate of enrollment, the enrollment period was found to be approximately, three years which would be followed by a minimum of one-year follow-up for the last subject randomized into the study. This will allow approximately 4 – 4.5 years of active follow-up of all randomized subjects followed by additional 2 years of passive follow-up using the VA databases. The total duration for the 16 participating sites will be approximately 6.5 years.

D. Statistical Analysis Plan

1. Intent-to-treat (ITT) analysis

Intent-to-treat population is defined as the population of subjects who will be randomized to either of the harvesting technique groups – EVH or OVH. The subjects will be categorized (in terms of their harvesting technique group assignment) based on their initial randomized group irrespective of conversion before surgery and will be included in analyses irrespective of their status – completer or drop out of the study before completion. Analyses of all outcome measures – primary and secondary – will use ITT population.

All statistical tests will be 2-sided and the primary MACE outcome will be tested at 5% level of significance. SAS will be used to conduct all the statistical analyses.

2. Primary Outcome Measure

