MACE, the composite endpoint that includes Death (all cause), Myocardial Infarction (MI) and Revascularization for myocardial ischemia, will be the primary outcome measure after randomization and the index CABG. Each randomized subject (either in Endoscopic or in Open harvesting group) will be followed after the index CABG to capture the time-to-MACE event where an ‘EVENT’ will be defined as either death (all cause) or an MI or a revascularization procedure during the follow-up period. Total follow-up period will be 6.5 years of which the first 4.5 years will be active follow-up (using in-clinic visit or by telephone) period and will be carried out by the site personnel. The remaining 2 years will be passive follow-up which will be carried out centrally by the chair’s office staff using the VA patient database. A minimum of 1 year of active follow-up will be used for subjects who will be randomized at the tail end of the 3-year projected enrollment period of the study. The subjects

who will either be lost to follow-up or will not experience an 'EVENT' before the end of the follow-up period will be considered as right censored.

The primary analysis of such time-to-Mace event data will include the events only from the active follow-up period (which is 4.5 years). The secondary analysis will include events from the entire 6.5 years of follow-up period.

Survival analysis techniques will be used to analyze the time-to-MACE event data for both primary and secondary analyses.

Kaplan-Meier analysis, a nonparametric method, will be used to estimate the survival (not experiencing MACE) over time in the two harvesting groups and a log-rank statistic will be used to test the equality of the survival function estimates in the two groups (the null hypothesis).

Cox's Proportional Hazards models will be used to investigate the effect of harvesting technique on the time until MACE adjusted for other potential influential variables, such as, age, gender, harvester's experience etc.

3. Secondary Outcomes Measures

One and Three-year MACE: This composite endpoint consists of

- i. Death (all cause);
- ii. Myocardial Infarction and
- iii. Revascularization for myocardial ischemia.

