7 STATISTICAL ANALYSES

7.1 Primary Outcome

The primary objective of this study is to investigate the impact of SVG harvesting techniques – OVH vs. EVH on MACE, a composite end point of all-cause mortality, nonfatal myocardial infarction and repeat revascularization, over the active follow-up period of the study postoperatively. The active follow-up time would begin with the first randomized patient and end after the last participant randomized has reached at least one-year of follow-up. Assuming the enrollment period is approximately three years, this would equate to approximately 4 to 4.5 years of active follow-up (in-clinic visit or contact by telephone carried out by site personnel), which will also be followed by two years of passive follow-up (carried out centrally by the chair's office staff using VA administrative databases). Thus, total follow-up time (active and passive) would be approximately 6.5 years. The primary outcome in the study is time (from index CABG surgery date) until the event of interest, MACE, or time-to-MACE during active follow-up (~4.5 years). Only the first event among participants will be considered as the MACE event.

To begin the analyses, the rate of MACE and its components (all-cause mortality, nonfatal myocardial infarction, & repeat revascularization) during active follow-up will be reported, both collectively and by SVG harvesting technique, OVH vs. EVH, considering only the first event so that components sum to total MACE (similar to TABLE 21). Survival analysis techniques will be employed to analyze the time-to-MACE data. Participants who are either lost-to-follow-up or did not experience a MACE event during the active follow-up period will be considered right-censored. Kaplan-Meier nonparametric survival estimates for risk of MACE will depict the unadjusted impact of SVG harvesting technique on MACE (FIGURE 2). Survival time represents time not experiencing a MACE. Tests of

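### The 97.5% power stated for the primary time-to-MACE test rests on an end-of-follow-up OVH rate (8.5%) below the one-year OVH rate (9.5%) assumed in the same section

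*Protocol*

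**What the plan says.** Protocol XVII.B contains two calculations.

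- **One year.** "To detect the expected 6 percentage point difference in one-year MACE rates between EVH (15.5%) and OVH (9.5" per cent), the section asks for 545 per group at 85% power with a two-sided 5% test. Inflated by 5% for drop-out, this gives about 1150.
- **End of active follow-up.** This point is placed at "approximately 4.5 years from the beginning of the recruitment process". Survival is defined there as not experiencing MACE, and the assumed survival proportions are "83.5% in the EVH and 91.5% in OVH), a sample size of 532 per group will be required to achieve a power of 97.5" per cent. The section concludes that 1150 subjects are enough for the time-to-MACE primary outcome.

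Three other statements fix how the two sets of rates must relate:

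- SAP 7.1: "Only the first event among participants will be considered as the MACE event".
- Minimum follow-up. In Protocol XVII.C the "enrollment period was found to be approximately, three years which would be followed by a minimum of one-year follow-up for the last subject randomized". In XVII.D.2, "A minimum of 1 year of active follow-up will be used for subjects who will be randomized at the tail end" of enrolment. In SAP 7.1 active follow-up is to "end after the last participant randomized has reached at least one-year of follow-up".
- Protocol III.D: "three-year composite MACE rates will be at least 8-10 percentage points lower in the open vein harvesting group" than in the endoscopic group.

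SAP 3.6 repeats only the one-year calculation. It neither restates nor corrects the 97.5%.

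**The concern.** The complements of 83.5% and 91.5% are cumulative MACE of 16.5% and 8.5%. Between one year and the end of follow-up, EVH therefore rises by one point (15.5% to 16.5%) while OVH falls by one point (9.5% to 8.5%). The composite is the same at both times and only first events count, so the OVH figure cannot go down.

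This is the only power statement for the primary log-rank test that I find in either document. If its inputs are impossible, the plan gives no usable power or expected event count for its main comparison, although about eight interim analyses of that outcome are planned (Protocol XVII.E, SAP 5.5).

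**Working it through.** **Inputs.** Protocol XVII.B: one-year MACE 15.5% (EVH) and 9.5% (OVH); end-of-follow-up MACE 16.5% and 8.5%; 532 per group. Protocol XVII.D: log-rank test, two-sided 5%. The protocol names no power method for the second calculation.

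**Formulas.** With p_E and p_O the MACE proportions and 532 per group:

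- HR (OVH vs EVH) = ln(1 − p_O) / ln(1 − p_E)
- events d = 532 × (p_E + p_O)
- Freedman power = Φ(√d × (1 − HR)/(1 + HR) − 1.96)

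**Step 1: reproduce the stated figure.** HR = ln(0.915)/ln(0.835) = 0.493. d = 532 × 0.25 = 133. √133 × (1 − 0.4926)/(1 + 0.4926) = 3.92, and 3.92 − 1.96 = 1.96, so power is 97.5%. The events needed for 97.5% are 132.98, or 531.9 per group. The exact match shows that these inputs produced the figure. (Schoenfeld gives 98.3%.)

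**Step 2: test the inputs against the one-year rates.**

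| | EVH with MACE | OVH with MACE | Total |
|---|---|---|---|
| Year one | 532 × 0.155 = 82.5 | 532 × 0.095 = 50.5 | 133 |
| End of active follow-up | 532 × 0.165 = 87.8 | 532 × 0.085 = 45.2 | 133 |

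The OVH arm would lose about five subjects with MACE. Reading 8.5% as a crude proportion does not help, because everyone has at least one year of follow-up. Reading it as a Kaplan-Meier estimate does not help either, because that survival estimate cannot rise over time.

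The total also stays at 133, so the extra follow-up adds no events. On the one-year rates HR = ln(0.905)/ln(0.845) = 0.593, and 133 events give 83.9% (Freedman) or 85.5% (Schoenfeld). The step from there to 97.5% comes only from moving one percentage point from OVH to EVH.

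**Step 3: same formula with possible end rates.** The 8-point gap is kept and OVH is at least 9.5%, so EVH is at least 9.5 + 8 = 17.5%.

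| EVH / OVH at end | HR | Events | Freedman power |
|---|---|---|---|
| 17.5% / 9.5% | 0.519 | 144 | 96.7% (maximum) |
| 20% / 12% | 0.573 | 170 | 94.3% |
| 25% / 17% | 0.648 | 223 | 89.2% |
| 30% / 22% | 0.697 | 277 | 84.5% |

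**Step 4: log-rank simulation with the one-year rates kept.** Settings: piecewise-exponential times, 532 per group, no drop-out, two-sided 5%, 4,000 to 8,000 runs (Monte Carlo standard error at most 0.8 points). Paired results are for follow-up uniform on 1–4 years and on 1.5–4.5 years, reflecting three-year accrual. All rates after year one are assumptions.

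- 8-point gap at three years: EVH 20%, 93.3/94.5%; EVH 25%, 88.9/90.9%; EVH 30%, 85.9/87.1%.
- 10-point gap at three years: 98.7/99.4%, 96.9/98.3% and 94.6/97.1% for the same EVH rates.
- One-year HR of 0.593 persisting, EVH hazard after year one of 1%, 3% or 5% a year: 88.0/87.8%, 91.2/92.9% and 94.1/96.1%. A repeat of the 1% case gave 87.5/88.3%.
- One-year hazards constant throughout: 99.3/99.8%.

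**The case against.** The strongest reply is that nothing in the plan depends on the figure. The target of 1150 is derived first, from the one-year calculation; SAP 3.6 keeps only that calculation; and no monitoring rule takes 133 events or 97.5% as an input. All of this stands. It limits the consequence but does not make the rates possible.

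The second reply is that the protocol concludes only that power is sufficient. At the most favourable possible pair with the 8-point gap (17.5%/9.5%) the loss is 97.5 − 96.7 = 0.8 points. This stands too: the scenarios above remain at about 84% or more.

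Protocol II reports another CSP 517 MACE result (4.8% OVH, 8.2% EVH), so the documents carry more than one OVH baseline. That does not cure the conflict, because XVII.B itself cites 9.9% from that study and plans on 9.5%.

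A reader might infer that the trial is underpowered, or that 97.5% is too high. The documents support neither. The later rates are not given, and some possible ones reach 97.5% or more. A reader might also cite power of about 62–81%, which results if the arms have equal hazards after year one (1–5% a year). That scenario shrinks the gap to 0.06 × exp(−2λ), or 5.9 to 5.4 points at three years, and to 5.8 to 5.0 points at 4.5 years. This contradicts both the 8-point end gap in XVII.B and the three-year hypothesis, so it is not a fair measure of this error.

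**Conclusion.** The point holds as an internal inconsistency between power inputs. It is not an arithmetic error. Given first-event counting and at least one year of follow-up for everyone, end-of-follow-up OVH MACE of 8.5% cannot coexist with 9.5% at one year, and the 97.5% has no valid basis.

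The size depends on later rates that the documents do not fix:

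- at most 96.7%, and 84.5% at 30%/22%, with crude end proportions and the 8-point gap;
- about 86–99% by simulation with an assumed 8–10 point gap at three years;
- about 87% to above 99% if the one-year hazard ratio persists, depending on the assumed later hazards.

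No single replacement figure can be given. The contradiction itself needs none of these assumptions.

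**What to change.** In Protocol XVII.B:

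1. Replace 83.5%/91.5% with end-of-follow-up rates no lower than the one-year rates: MACE of at least 15.5% (EVH) and 9.5% (OVH), and at least 17.5% for EVH if the 8-point gap is kept. Make them consistent with the three-year hypothesis.
2. In place of 97.5%, state log-rank power and expected events as a short range over explicit later-rate assumptions. Any scenario with no effect after year one should be left out, or labelled as contradicting the plan's own gap.

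The cost is one recalculation and a wording change. The stated power may look less favourable. The target of 1150 and the analysis do not change.

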The other secondary outcome measures are MACE at one and three-year post surgery, leg wound healing complications and Quality of Life.

Two leading vendors (Maquet and Terumo) are currently marketing EVH device technologies for CABG. Device-related and procedural information will be collected during the study.

Subjects will receive concomitant optimal medical therapies (OMT) in both groups as recommended by the current 2011 American College of Cardiology/American Heart Association guidelines [Smith 2011]. OMT will include formal smoking cessation counseling and the administration of aspirin, beta blockers, angiotensin converting enzyme inhibitors, and lipid-lowering medications.

FIGURE 1. STUDY FLOW DIAGRAM

VI. Subject Population

All subjects who are candidates for CABG and who will undergo surgery at a VAMC with demonstrated expertise for both OVH and EVH and qualify to participate in CSP-sponsored research will be invited to participate in the REGROUP study.

A. Inclusion Criteria:

- Age 18 years or older
- Elective or Urgent CABG-only
- Median sternotomy approach
- At least one coronary bypass planned using saphenous vein graft for conduit
- Experienced EVH/OVH harvester and participating surgeon available for procedure

B. Exclusion Criteria:

- Combined valve procedure planned
- Moderate or severe valve disease (see definition of moderate/severe valve)
- Hemodynamically unstable or in cardiogenic shock
- Enrolled in another therapeutic or interventional study
- Off-pump CABG procedure planned
- Limited life expectancy < 1 year
- History of lower extremities venous stripping or ligation
- Inability to provide informed consent

C. Recruitment and Screening

We propose a prospective, multicenter, two-arm, randomized clinical trial (RCT). A block randomization technique will ensure equal distribution of subjects, within each harvester, within each site, in both arms of the trial. The randomization schema will be generated using SAS (SAS, Cary, NC).

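### The 97.5% power for the primary time-to-MACE test ignores staggered entry and rests on rates that conflict with the plan's one-year rates; it should be recomputed for the actual design

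*Protocol*

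**What the plan says.** Protocol XVII.B contains two calculations. The first is for one-year MACE, 15.5% with EVH against 9.5% with OVH. It gives 545 per group at 85% power and, after 5% inflation, about 1150 subjects. SAP 3.6 repeats only this one.

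The second is for the primary time-to-event outcome. It takes MACE-free proportions of "83.5% in the EVH and 91.5% in OVH", placed "at the end of the active follow-up period (approximately 4.5 years from the beginning of the recruitment process"), and states that "a sample size of 532 per group will be required to achieve a power of 97.5" per cent. From this it concludes that 1150 subjects, with about 7% attrition, are adequate for the primary outcome. It names no formula, event count, accrual pattern or hazard shape.

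On follow-up, XVII.C describes about three years of enrolment and then at least one year for the last subject, and continues: "This will allow approximately 4 – 4.5 years of active follow-up of all randomized subjects". XVII.D.2 says "A minimum of 1 year of active follow-up will be used for subjects who will be randomized at the tail end" of enrolment. SAP 7.1 defines the window for the whole study: "The active follow-up time would begin with the first randomized patient and end after the last participant randomized has reached at least one-year of follow-up".

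On the test, XVII.D.1 says "All statistical tests will be 2-sided and the primary MACE outcome will be tested at 5% level of significance". XVII.D.2 names the log-rank statistic. Allocation is equal (VI.C).

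**The concern.** Individual follow-up cannot be 4 to 4.5 years for everyone if subjects enter over three years and active follow-up stops at a common close-out. Only the first subjects come near that horizon. The sentence in XVII.C conflicts with the one before it, with XVII.D.2 and with SAP 7.1.

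The power statement appears to share the assumption. If it does, it describes a trial with 4.5 years per subject, which is 4.5/3.0 = 1.5 to 4.5/2.5 = 1.8 times the planned average exposure. It is the only power given for the primary outcome in either document, and neither document states an expected number of primary events. The protocol also foresees about eight interim analyses of this outcome and suggests Lan-DeMets boundaries, for which a planned event total would be useful.

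**Working it through.** **Inputs.** MACE-free 83.5% (EVH) and 91.5% (OVH), about 4.5 years, 532 per group, 97.5% (XVII.B); two-sided 5% (XVII.D.1); 1:1 (VI.C); log-rank (XVII.D.2); three-year accrual with at least one year for the last subject (XVII.C, XVII.D.2, SAP 7.1).

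**Step 1: reproduce the plan's figure.** Cumulative hazards are −ln(0.835) = 0.1803 and −ln(0.915) = 0.0888, so HR (EVH to OVH) = 2.030. Freedman's formula gives

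D = (1.96 + 1.96)² × ((HR + 1)/(HR − 1))² = 15.37 × 8.654 = 133 events,

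and 133/(0.165 + 0.085) = 532 per group, exactly as printed. Schoenfeld's formula gives 492 and the two-proportion formula 522 (547 with continuity correction), so Freedman is the match. No accrual or censoring term enters.

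**Step 2: follow-up under the design.** With uniform three-year entry and close-out one year after the last entry, follow-up is 1 to 4 years (mean 2.5). If close-out is at 4.5 years, it is 1.5 to 4.5 years (mean 3.0).

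**Step 3: constant hazard (an assumption), printed rates held at 4.5 years.** The hazards are λ = 0.1803/4.5 = 0.0401 and 0.0888/4.5 = 0.0197 per year. With minimum follow-up F, the event probability per arm is 1 − [exp(−λF) − exp(−λ(F + 3))]/(3λ).

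- F = 1: 0.0948 and 0.0480, so 532 × (0.0948 + 0.0480) = 76 events.
- F = 1.5: 0.1127 and 0.0574, giving about 90 events.

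Power = Φ(√D × (HR − 1)/(HR + 1) − 1.96) = Φ(0.340√D − 1.96), which is 84.2% and 89.9%. Log-rank simulation (4000 runs each) gives 85.0% and 91.3%; with a fixed 4.5 years it gives 97.6%. With all 575 per arm retained, the formula gives 82 to 98 events and 87% to 92%.

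**Step 4: front-loaded hazards, same rates at 4.5 years, 532 per arm.**

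| Hazard shape (assumed) | 1–4 years | 1.5–4.5 years |
|---|---|---|
| Constant | 76 events, 84% | 90 events, 90% |
| Weibull, shape 0.7 | 89 events, 89% | 101 events, 93% |
| Weibull, shape 0.5 | 99 events, 92% | 109 events, 94% |
| 93% of hazard in year one | 128 events, 97.0% | 129 events, 97.2% |

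The last row takes its share from the plan's own EVH figures: ln(0.845)/ln(0.835) = 0.93.

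**Step 5: consistency with the one-year rates.** A constant hazard through the 4.5-year rates implies one-year MACE of 1 − 0.835^(1/4.5) = 3.9% and 1 − 0.915^(1/4.5) = 2.0%, against 15.5% and 9.5% in the same section. For OVH no curve fits both sets, since cumulative MACE cannot fall from 9.5% at one year to 8.5% later. The one-year rates alone give 532 × (0.155 + 0.095) = 133 events by year one. Their hazard ratio is ln(0.845)/ln(0.905) = 1.69, and 133 events at that ratio give 83.9% power (Freedman).

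**The case against.** The strongest defence is that XVII.B counts its 4.5 years from the start of recruitment and defines the figures as proportions of subjects without MACE at the end of active follow-up. The primary hypothesis is also worded as a proportion over that period. Read as crude proportions at close-out, staggered entry is already in the rates, and 133 events and 97.5% follow. That reading is open and the arithmetic is right. It does not rescue the figure: every subject is planned to have at least one year, and by then the same section expects 9.5% MACE with OVH, so 8.5% at close-out is impossible on that reading too. The sentence in XVII.C remains wrong in any case.

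A reader might go further and infer that the plan's own inputs yield only 76 to 90 events and 84% to 90% power, or that the trial is underpowered. The documents do not support this. Those figures need a constant hazard that the plan never states and that contradicts its one-year rates. The two ends also belong to different close-outs: 76 events to a mean follow-up of 2.5 years, 90 to a mean of 3.0. With events concentrated in year one the loss is under one point. Even the lowest value, 84%, is close to the 85% used for the one-year comparison, which is where 1150 comes from.

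Nor do the documents use 133, or any other count, as planned information for the interim looks. What stands there is that no event total is given.

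**Conclusion.** The point holds as a defect in the stated power, not as evidence of too small a trial. The 97.5% is a fixed-follow-up Freedman result, while the design gives about 1 to 4–4.5 years of active follow-up per subject. With the printed rates at 4.5 years, 532 per arm, uniform accrual and proportional hazards, the overstatement runs from under 1 point (93% of the hazard in year one) to about 13 points (constant hazard, 1 to 4 years). The documents do not fix a value in that range, because they state no hazard shape and their 4.5-year OVH rate is incompatible with their one-year OVH rate. The claim in XVII.C about all randomized subjects is wrong whatever the hazard shape.

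**What to change.** In XVII.B, replace 97.5% with a log-rank power computed for the stated design: 36-month accrual, 12-month minimum follow-up to a common close-out, and the stated attrition. Use an event curve consistent with 15.5% and 9.5% at one year. State the hazard assumption and the expected number of primary events. In XVII.C, say that active follow-up per subject runs from about 1 to 4–4.5 years. Carry the power and event count into SAP 3.6.

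Do not print 84–90% or 76–90 events as the replacement, and do not use 76–90 as planned interim information: both conflict with the 133 events that the one-year rates alone give.

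The cost is a recalculation and wording in two documents. No extra patients or procedures are needed, and 1150 stands. The stated power will probably be less favourable, but how much depends on what is assumed after year one.
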